## 6.7 Compensation for Research-Related Injury

Does the research involve greater than minimal risk to subjects? (*or if minimal risk, is there potential risk of research-related injury?*):

Yes  No

There is no plan to compensate volunteers for any injury incurred as a result of participation in this study. Volunteers and/or their insurance companies will be responsible for any charges for treatment of research-related injuries, and will have reviewed and consented to this in the screening and main ICFs.

## 6.8 Economic Burden to Subjects

Does the research involve any costs to subjects?

Yes  No

## 6.10 Vulnerable Populations

*If the research involves individuals who are vulnerable to coercion or undue influence, describe the rationale for their inclusion and the additional safeguards included to protect their rights and welfare.*

Will pregnant women be enrolled?

Yes  No

Will the research involve neonates of uncertain viability or non-viable neonates?

Yes  No

•

Will subjects who are not yet adults (neonates, children, teenagers) be enrolled?

Yes  No

• Will minors who are:

- i) married, widowed, divorced; or
- ii) the parent of a child; or
- iii) a member of any of the armed forces; or
- iv) pregnant or believes herself to be pregnant; or
- v) living separate and apart from his/her parent or legal guardian, and is managing his/her own financial affairs

be approached for study participation for either themselves or their child?

Yes  No

Will wards of the state and/or children at risk of becoming wards of the state be enrolled (this includes foster children or any child that is in state custody)?

Yes  No

• Will cognitively impaired adults (adults with impaired-decision making capacity) or adults who may lose the capacity to consent be enrolled?

Yes  No

○ Will prisoners be enrolled?

Yes  No

Will students and/or employees be enrolled in this research?

Yes  No

Although students and employees will not be targeted for recruitment and enrollment, employees of Tufts University and/or the HNRCA (employee-subjects) who voluntarily want to participate in the study will be eligible for screening and enrollment. In order to qualify for the study, employee-subjects must respond to IRB-approval advertisement of their own accord and will not be directly approached by any person seeking to recruit them for participation in the study. Members of the research team, as direct-report subordinates of the PI and anyone who is direct-report subordinate to any of the research team members in any other capacity and staff and scientists who are primarily trained in nutrition will not be eligible to participate in the study. If employee-subjects qualify to participate in the study, they cannot participate as volunteers during hours in which they are being compensated by Tufts University for their regular work. This includes use of vacation, personal days and sick time.

## 7 Adverse Event Monitoring

### 7.1 Definitions

An adverse event (AE) is any untoward medical occurrence in a human subject, including any abnormal sign (for example, abnormal physical exam or laboratory finding), symptom, or disease, temporally associated with the subject's participation in the research, whether or not considered related to the subject's participation in the research. An AE is therefore any unfavorable and unintended sign (including an abnormal laboratory finding), symptom or disease temporally associated with the administration of an investigational product, whether or not related to that investigational product. An unexpected AE is one of a type not identified in nature, severity, or frequency in the current Investigator's Brochure or of greater severity or frequency than expected based on the information in the Investigator's Brochure.

The Investigator will probe, via discussion with the subject, for the occurrence of AEs during each subject visit and record the information in the site's source documents for both Parts 1 and 2. Adverse events will be recorded in the patient CRF. Adverse events will be described by duration (start and stop dates and times), severity, outcome, treatment and relation to study drug, or if unrelated, the cause.

#### AE Severity

The National Cancer Institute's Common Terminology Criteria for Adverse Events (CTCAE) Version 3.0 should be used to assess and grade AE severity, including laboratory abnormalities judged to be clinically significant. The modified criteria can be found in the study manual. If the experience is not covered in the modified criteria, the guidelines shown in

Table 1 below should be used to grade severity. It should be pointed out that the term "severe" is a measure of intensity and that a severe AE is not necessarily serious.

Table 1. AE Severity Grading

Severity (Toxicity Grade)	Description
Mild (1)	Transient or mild discomfort; no limitation in activity; no medical intervention or therapy required. The subject may be aware of the sign or symptom but tolerates it reasonably well.
Moderate (2)	Mild to moderate limitation in activity, no or minimal medical intervention/therapy required.
Severe (3)	Marked limitation in activity, medical intervention/therapy required, hospitalizations possible.
Life-threatening (4)	The subject is at risk of death due to the adverse experience as it occurred. This does not refer to an experience that hypothetically might have caused death if it were more severe.

### AE Relationship to Study Drug

The relationship of an AE to the study drug should be assessed using the following the guidelines in Table 2.

Table 2. AE Relationship to Study Drug

Relationship to Drug	Comment
Definitely	Previously known toxicity of agent; or an event that follows a reasonable temporal sequence from administration of the drug; that follows a known or expected response pattern to the suspected drug; that is confirmed by stopping or reducing the dosage of the drug; and that is not explained by any other reasonable hypothesis.
Probably	An event that follows a reasonable temporal sequence from administration of the drug; that follows a known or expected response pattern to the suspected drug; that is confirmed by stopping or reducing the dosage of the drug; and that is unlikely to be explained by the known characteristics of the subject's clinical state or by other interventions.
Possibly	There is a reasonable possibility that the adverse event, incident, experience or outcome may have been caused by the procedures involved in the research.
Unrelated	An event that can be determined with certainty to have no relationship to the study drug.

### Serious Adverse Experiences (SAE)

An SAE is defined as any AE occurring at any dose that results in any of the following outcomes:

- death
- a life-threatening adverse experience
- inpatient hospitalization or prolongation of existing hospitalization
- a persistent or significant disability/incapacity
- a congenital anomaly/birth defect

Other important medical events may also be considered an SAE when, based on appropriate medical judgment, they jeopardize the subject or require intervention to prevent one of the outcomes listed.

### 7.2 Reporting Procedures

Serious adverse events (SAE) and unanticipated events (UE) will be reported by participants as soon as practically possible and investigators will report these to the IRB within 24 hours of study team becoming

aware of event. The definition and reporting requirements for SAEs and UEs will adhere to Tufts University policies. All SAE and UE will be reviewed by the study physician and an event evaluation form will be completed that will include a description of the event, assessment of potential relationship to the intervention, assessment of need for change in the consent or the study activities, event outcome and a classification of the main organ system involved. Raw data will be available for review by the Study Physician if requested.

An adverse event is defined as: “Any untoward or unfavorable medical occurrence in a human research participant, including any abnormal sign (e.g., abnormal physical exam or laboratory finding), symptom, or disease, temporally associated with the individual’s participation in the research, whether or not considered related to the individual’s participation in the research.”

Reporting timeframe for SAEs and AEs:

Investigators will promptly report unexpected adverse events, serious adverse events, unanticipated problems involving risk to subjects or others, and deviations to IRB within five business days using the Reportable New Information (HRP-214) form. The study physician will be notified of potential unexpected study-related events, and serious adverse events that may possibly be related to the study for further classification. All other adverse events will be reported to the Tufts Institutional Review Board at the time of continuing review. If adverse event monitoring suggests that events are occurring with greater frequency or severity than initially expected, the PI will submit a report of an Unanticipated Problem to the IRB, with an amendment if a modification of the study design is indicated.

### **7.3 Reportable New Information**

Reportable new information will be reported to the IRB per the Tufts Health Sciences IRB’s [Reportable New Information policy](#).

## **8 Statistical Considerations**

### **8.1 Study Endpoints**

#### **Part 1:**

- Primary Endpoint

To determine whether SLC19A3 inhibitors metformin and/or trimethoprim decreases the AUC, area under the curve, of thiamine between the different treatment groups, thiamine versus thiamine and SLC19A3 inhibitor. This endpoint will be assessed at the end of Part 1 using all data available across all three groups, specifically comparing data from the thiamine only arm against the thiamine and SLC19A3 inhibitor combination arms. A decrease in AUC in the combination treatment will suggest inhibition of thiamine uptake through inhibition of SLC19A3.

- Secondary Endpoint

Investigate metabolic signatures reflecting the activity of TPP-dependent enzymes after dosing thiamine versus combination of thiamine and SLC19A3 inhibitor. Thiamine pyrophosphate (TPP), one of the major metabolites of thiamine, is a co-factor for multiple metabolic pathways. Thus, it is possible that a decrease in thiamine absorption by metformin could affect the concentration of key metabolites and metabolic ratios of TPP-dependent enzymes and pathways.

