#### **Part 2:**

- Primary Endpoint

To confirm whether trimethoprim affects the AUC, area under the curve, of thiamine between the different treatment groups, thiamine versus thiamine and trimethoprim. This endpoint will be assessed at the end of Part 2 using all data available across both groups from both Parts 1 and 2, specifically comparing data from the thiamine only arm against the thiamine and trimethoprim combination arm. A decrease in AUC in the combination treatment will suggest inhibition of thiamine uptake through inhibition of SLC19A3.

- Secondary Endpoint

Further investigate metabolic signatures reflecting the activity of TPP-dependent enzymes after dosing thiamine versus combination of thiamine and trimethoprim. Thiamine pyrophosphate (TPP), one of the major metabolites of thiamine, is a co-factor for multiple metabolic pathways. Thus, it is possible that a decrease in thiamine absorption by trimethoprim could affect the concentration of key metabolites and metabolic ratios of TPP-dependent enzymes and pathways.

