## 8.2 Statistical Analysis

### Analysis of Primary Endpoint

For Part 1 and Part 2, pharmacokinetic parameters including half-life, apparent volume of distribution\*, total clearance\*, renal clearance, net reabsorptive or secretory clearance, absorption rate constant,  $K_a$ , and  $AUC_{po}$  of thiamine and the respective SLC19A3 inhibitor will be calculated from plasma and urine drug and vitamin levels by standard pharmacokinetic methods using WinNonlin (\*these parameters are divided by bioavailability as oral doses are given). We will estimate glomerular filtration rate, GFR, using standard methods described in our previous studies. To assess net secretory or reabsorptive clearance of the compounds, we will subtract  $fu^*GFR$  (where  $fu$  is the unbound fraction of metformin, thiamine, TMP or TPP) from renal clearance of the compounds directly measured from plasma and urine values. Previously we have used these methods to calculate net secretion (or reabsorption) of several drugs. In addition, for TMP and TPP, half-life,  $AUC_{po}$ , renal clearances, net reabsorptive or secretory clearance, and ratios of AUCs of TMP and TPP to thiamine will be calculated using standard pharmacokinetic methods for metabolites.

For statistical analysis, we will use paired-t-tests to compare the pharmacokinetic parameters of thiamine in the absence and presence of an SLC19A3 inhibitor. In the pharmacokinetic analyses, we expect to see a significant influence of the SLC19A3 inhibitor on the oral exposure to thiamine,  $AUC_{po}$ . Because SLC19A3 in the proximal tubule mediates reabsorption of thiamine, we may also observe an increase in the renal clearance (reduction in reabsorptive clearance) of thiamine when volunteers are dosed with an SLC19A3 inhibitor. Understanding the effect of metformin and/or trimethoprim on renal clearance of thiamine is also of interest and could potentially contribute to even lower plasma thiamine levels.

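### Does Section 8.1 need a renal-clearance condition before a fall in thiamine AUC is read as reduced uptake?

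*Combined protocol and SAP*

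**What the plan says.** The primary endpoint in each part (Section 8.1) is the change in thiamine AUC between thiamine alone and thiamine plus inhibitor. The stated reading is the same in both parts: "A decrease in AUC in the combination treatment will suggest inhibition of thiamine uptake through inhibition of SLC19A3". The Part 2 assessment is made "using all data available across both groups from both Parts 1 and 2".

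The primary objectives in Section 3 concern absorption and distribution, and they rest on AUC together with other pharmacokinetic parameters.

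Section 8.2, under the heading for the primary-endpoint analysis, plans "pharmacokinetic parameters including half-life, apparent volume of distribution", total and renal clearance, and net reabsorptive or secretory clearance. The net figure starts from "renal clearance of the compounds directly measured from plasma and urine values". On testing it says: "we will use paired-t-tests to compare the pharmacokinetic parameters of thiamine in the absence and presence of an SLC19A3 inhibitor". It then raises the renal route itself: "Because SLC19A3 in the proximal tubule mediates reabsorption of thiamine", "we may also observe an increase in the renal clearance (reduction in reabsorptive clearance) of thiamine". It adds that this "could potentially contribute to even lower plasma thiamine levels".

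Urine is collected over 0-24 h in four intervals in each part (Section 5.3).

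**The concern.** With oral dosing only, AUC depends on bioavailability and on clearance, so AUC alone cannot separate less absorption from faster elimination. The plan names a second route to a lower AUC, yet Section 8.1 sets no condition on renal clearance. Section 8.2 treats the renal effect as an addition to an absorption effect rather than as an alternative explanation. No section says how a fall in AUC with raised renal clearance will be read.

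At stake is the label on the result. The objectives name absorption, the secondary objectives look for signatures of reduced absorption, and Section 2.1 wants the findings to inform dosing of concomitant medications in at-risk populations. A fall that is partly renal could carry the wrong label into all three.

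**Working it through.** The plan gives no figure to reproduce. It states target completers (6 in Part 1, 12 in Part 2, so 18 together) but no effect size, variability or renal share of clearance. The figures below are illustrations on assumed inputs.

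**1. Can AUC alone mislead?** Let fr be the renal share of clearance, k and q the fold changes in renal and non-renal clearance, and F the absorption ratio. Then:

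- total clearance ratio c = fr·k + (1 − fr)·q
- AUC ratio = F/c
- urinary recovery ratio = k·F/c
- V/F ratio = 1/F
- half-life ratio = 1/c

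| Mechanism | Inputs | AUC | Renal clearance | Recovery | V/F | Half-life |
|---|---|---|---|---|---|---|
| Less absorption | F = 1/1.3, c = 1 | 0.77 | 1.00 | 0.77 | 1.30 | 1.00 |
| Renal only | fr 0.6, k 1.5: c = 0.9 + 0.4 = 1.3 | 0.77 | 1.50 | 1.15 | 1.00 | 0.77 |
| Non-renal clearance up | fr 0.4, q 1.5: c = 0.4 + 0.9 = 1.3 | 0.77 | 1.00 | 0.77 | 1.00 | 0.77 |

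Yes, AUC alone can mislead. Over fr 0.2 to 0.8 and k 1.25 to 2, with F = q = 1, a purely renal effect lowers AUC by between 1 − 1/1.05 = 4.8% and 1 − 1/1.8 = 44.4%.

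**2. Does the plan hold what separates the mechanisms?** Renal clearance isolates the second row. Half-life and V/F separate the third row from the first. Section 8.2 lists all three. Urinary recovery needs no new sample, because it equals renal clearance times AUC over the same interval.

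**3. Would a fixed rule do better?** Take the rule that absorption is called not established when AUC falls, the renal clearance interval lies above 1 and the recovery interval does not lie below 1. Simulation: 40,000 trials per cell, paired log ratios, SD of difference √(2·ln(1 + 0.30²)) = 0.415, correlation 0.5 between AUC and recovery, t-based 95% intervals.

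- Renal only (second row): the AUC interval lies below 1 in about 24% / 52% of trials with 6 / 12 completers. The rule triggers in about 70% / 94% of those.
- Absorption loss only (F = 0.70), 12 completers: the AUC interval lies below 1 in about 77%. The rule triggers wrongly in about 2% of those.
- Both effects (F = 0.70, fr 0.4), 12 completers: c = 1.1 / 1.2 / 1.4 at k 1.25 / 1.5 / 2, so AUC ratios are 0.64 / 0.58 / 0.50 and recovery ratios 0.80 / 0.88 / 1.00. Absorption is called not established in about 28% / 74% / 97% of trials, although 30% of it is truly lost.
- Non-renal clearance up (third row): the rule triggers in about 5% / 4% of AUC-positive trials with 6 / 12 completers, so it passes nearly all of them.

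**The case for a change.** The best case for a change is that the study's inference does not stop at the transporter. Absorption is the word in the objectives and the secondary endpoints, and a reading written before results are seen is worth more than one written after. A linking sentence would need no new samples or subjects, and it would not create false alarms when absorption alone is affected.

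Two parts of this stand. The linking sentence is not written anywhere. And in a study this small, a renal clearance result that is not significant does not exclude a renal share: with both CVs at 30%, its 95% interval spans a factor of about 1.55 either way with 6 completers, 1.30 with 12 and 1.23 with 18. Whoever writes the report should say so.

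The rest does not carry. The Section 8.1 sentence speaks of uptake through SLC19A3, not of intestinal absorption, and a renal effect would still be SLC19A3 inhibition. To report a wholly renal fall as lost absorption, the authors would have to ignore a comparison planned under the same endpoint and a mechanism they describe themselves. A firm rule also costs most in the very case Section 8.2 foresees, where the renal effect adds to the absorption effect.

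Adopting such a rule would also force a choice on endogenous thiamine. If baseline made up an assumed 30% of uncorrected AUC and did not change, a true ratio of 0.70 would appear as 0.30 + 0.70 × 0.70 = 0.79. That is a separate question, and the simulation above leaves baseline out.

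**Conclusion.** The plan can stand as written. This is a gap in linkage that analysts fill sensibly: Section 8.1 gives a hedged reading, and Section 8.2 names the competing route, derives the quantities that distinguish it and plans the paired comparisons. The reading of AUC alongside renal clearance, recovery, half-life and V/F belongs in the report's discussion and needs no new analysis. A pointer from Section 8.1 to Section 8.2 would be harmless but editorial. A binding rule would trade protection against one mislabelling for frequent failure to report a true absorption loss, and would still miss a non-renal change in clearance.

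The AUC comparison, the sample size and a conclusion of SLC19A3 inhibition are untouched. The sizes quoted rest on assumed values for the renal share, the fold changes, the CVs and their correlation, none of which the documents give. The linkage argument does not depend on them.

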#### **Part 2:**

- Primary Endpoint

To confirm whether trimethoprim affects the AUC, area under the curve, of thiamine between the different treatment groups, thiamine versus thiamine and trimethoprim. This endpoint will be assessed at the end of Part 2 using all data available across both groups from both Parts 1 and 2, specifically comparing data from the thiamine only arm against the thiamine and trimethoprim combination arm. A decrease in AUC in the combination treatment will suggest inhibition of thiamine uptake through inhibition of SLC19A3.

- Secondary Endpoint

Further investigate metabolic signatures reflecting the activity of TPP-dependent enzymes after dosing thiamine versus combination of thiamine and trimethoprim. Thiamine pyrophosphate (TPP), one of the major metabolites of thiamine, is a co-factor for multiple metabolic pathways. Thus, it is possible that a decrease in thiamine absorption by trimethoprim could affect the concentration of key metabolites and metabolic ratios of TPP-dependent enzymes and pathways.

## 8.2 Statistical Analysis

### Analysis of Primary Endpoint

For Part 1 and Part 2, pharmacokinetic parameters including half-life, apparent volume of distribution\*, total clearance\*, renal clearance, net reabsorptive or secretory clearance, absorption rate constant,  $K_a$ , and  $AUC_{po}$  of thiamine and the respective SLC19A3 inhibitor will be calculated from plasma and urine drug and vitamin levels by standard pharmacokinetic methods using WinNonlin (\*these parameters are divided by bioavailability as oral doses are given). We will estimate glomerular filtration rate, GFR, using standard methods described in our previous studies. To assess net secretory or reabsorptive clearance of the compounds, we will subtract  $fu^*GFR$  (where  $fu$  is the unbound fraction of metformin, thiamine, TMP or TPP) from renal clearance of the compounds directly measured from plasma and urine values. Previously we have used these methods to calculate net secretion (or reabsorption) of several drugs. In addition, for TMP and TPP, half-life,  $AUC_{po}$ , renal clearances, net reabsorptive or secretory clearance, and ratios of AUCs of TMP and TPP to thiamine will be calculated using standard pharmacokinetic methods for metabolites.

For statistical analysis, we will use paired-t-tests to compare the pharmacokinetic parameters of thiamine in the absence and presence of an SLC19A3 inhibitor. In the pharmacokinetic analyses, we expect to see a significant influence of the SLC19A3 inhibitor on the oral exposure to thiamine,  $AUC_{po}$ . Because SLC19A3 in the proximal tubule mediates reabsorption of thiamine, we may also observe an increase in the renal clearance (reduction in reabsorptive clearance) of thiamine when volunteers are dosed with an SLC19A3 inhibitor. Understanding the effect of metformin and/or trimethoprim on renal clearance of thiamine is also of interest and could potentially contribute to even lower plasma thiamine levels.

### Analysis of Secondary Endpoint

For the metabolic signatures, results will be processed with pair-wise mean testing, hierarchical cluster analyses, and multivariate discriminant analyses while employing multiple comparison corrections, as appropriate. Basal thiamine status including transketolase activity will be evaluated as a covariate prior to all analyses. Our primary analyses will focus on comparing the levels of the individual metabolites and metabolite ratios after vitamin administration with the baseline levels to determine if there are effects of the vitamin on the metabolite levels and ratios in the plasma. The primary comparison will test differences between treatments using one-way ANOVA with Holm-Sidak post hoc comparison, or Student's t-Tests with the False Discovery Rates adjustment of Benjamini and Hochberg. For Part 1 and Part 2, our second comparison will be to compare the levels of metabolites after thiamine administration with their levels after thiamine plus SLC19A3 inhibitor administration at multiple time points. To identify discriminants of thiamine vs. thiamine + SLC19A3 inhibitor exposure, all variables will be transformed to normality and subjected to orthogonal partial least squares – discriminant analysis (OPLS-DA) and boot strapped models will be built with a 3:1 training/test set splits using the imDEV v 1.4.268. Variables with variable importance in projection (VIP) scores <1 will be removed from further consideration, and models refined to minimize the root-mean-squared-error of prediction (RMSEP) and maximize Q2, a measure of model performance. The retained variable set will be organized using hierarchical cluster analysis. To test for significance of discriminant variables of thiamine or SLC19A3 inhibitor effects, including levels of metabolites or metabolic ratios, we will compare levels of retained metabolites (or ratios) at each time after vitamin or drug administration with baseline values, using paired-t- tests, and among times and treatments using two-way ANOVAs with Holm-Sidak post hoc comparison. To assess covariate behavior among thiamine, TPP, metformin, other metabolites and/or or metabolite ratios, hierarchical cluster

analyses will be performed and Spearman's correlation matrices will be generated. Linear correlation analyses will be conducted, and correlation coefficients will be estimated for each metabolite in each volunteer (in each study arm). To compare time-dependent changes in each study arm, in addition to our pharmacokinetic analysis, plasma thiamine will first be modeled as a continuous variable using partial least squares discriminant analysis, and variables with variable importance in projection scores (VIP) >1 will be selected. The average metabolite value will then be independently calculated in each study arm, and variables will be organized in the self-organizing maps using the Kohonen package in R70. Patterns will be compared between treatment groups by regression analysis of representative variable group members. Additional complex relationships will be examined if the data warrant those, for example, Emax models may be used to characterize the relationship between thiamine levels and levels of metabolites or metabolic ratios.

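### Metabolite treatment tests in this crossover are named without pairing or a subject term, and before-after change is read as a vitamin effect although every cycle contains thiamine

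*Combined protocol and SAP*

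**What the plan says.** Section 5.1 describes two randomised crossovers. Each Part 1 subject receives thiamine alone, thiamine with metformin and thiamine with trimethoprim. Each Part 2 subject receives thiamine alone and thiamine with trimethoprim. Section 8.3 aims for 6 completers in Part 1 and 12 in Part 2.

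For metabolites, Section 8.2 (Analysis of Secondary Endpoint) says:

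- In general terms, "results will be processed with pair-wise mean testing".
- For treatment differences, "The primary comparison will test differences between treatments using one-way ANOVA with Holm-Sidak post hoc comparison", or else Student's t-tests with a false discovery rate adjustment.
- For retained variables, post-dose values are compared with baseline "using paired-t- tests, and among times and treatments using two-way ANOVAs with Holm-Sidak post hoc comparison". This follows a selection step: "Variables with variable importance in projection (VIP) scores <1 will be removed from further consideration".
- On covariates, "Basal thiamine status including transketolase activity will be evaluated as a covariate prior to all analyses".
- On ranking, "Our primary analyses will focus on comparing the levels of the individual metabolites and metabolite ratios after vitamin administration with the baseline levels", with the purpose "to determine if there are effects of the vitamin on the metabolite levels and ratios in the plasma". The between-treatment test is then also called primary, while for thiamine against thiamine plus inhibitor "our second comparison will be to compare the levels of metabolites after thiamine administration".

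The Analysis of Primary Endpoint in the same section names paired t-tests for thiamine pharmacokinetics with and without an inhibitor. The secondary objectives in Section 3 compare metabolites after thiamine alone with metabolites after the combination.

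**The concern.** There are two substantive issues and one editorial one.

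1. **Pairing.** The metabolite treatment tests are named in their ordinary form for data in which the same people supply every treatment. The plan writes the word paired where it means it, for pharmacokinetics and for metabolites against baseline, but not here. An analyst who runs the tests as named leaves between-subject variation in the error term. With 6 and 12 completers, that could hide real differences in a biomarker search.
2. **Attribution.** A change from the pre-dose sample is to be taken as showing what the vitamin does. No listed cycle omits thiamine, so anything else that changes after the morning baseline would be credited to it.
3. **Ranking.** Primary status is given to two different comparisons, and the contrast that matches the stated objective is called the second. The sentences can be reconciled, but the plan does not do so.

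**Working it through.** **Inputs.** From the documents: every subject receives every treatment (5.1); 6 and 12 completers (8.3); the tests named in 8.2. The documents give no alpha, power, effect size, SD or within-subject correlation for this endpoint, so there is no stated figure to reproduce. Assumed: normal data, two-sided 5% per test before multiplicity correction, a shared subject effect, and a difference δ of 0.8 total SD unless stated. The within-subject correlation ρ is varied.

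**Why pairing matters.** With total SD 1, the variance of the difference between two treatment means is 2(1−ρ)/n. The ordinary t-test estimates it as about 2/n, so its standard error is too large by a factor of 1/√(1−ρ). At ρ = 0.5 this is 1.41.

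**Paired power.** The noncentrality is δ√n / √(2(1−ρ)) on n−1 df. For n = 12, δ = 0.8, ρ = 0.5: 0.8 × 3.464 / 1 = 2.77 on 11 df, giving 71%.

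**Simulation** (t-tests 200,000 runs per cell; ANOVA 100,000 runs per cell, with one of three treatments shifted):

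| Test | ρ | Power, ordinary | Power, paired or repeated-measures | Type I error, ordinary |
|---|---|---|---|---|
| t, n = 12 (Part 2) | 0 | 46.6% | 43.3% | 5.0% |
| | 0.3 | 46.0% | 56.7% | 2.1% |
| | 0.5 | 45.6% | 71.3% | 0.9% |
| | 0.7 | 45.5% | 90.2% | 0.2% |
| t, n = 6 (Part 1) | 0 | 24.1% | 20.6% | 5.1% |
| | 0.3 | 21.3% | 27.1% | 2.4% |
| | 0.5 | 19.2% | 35.7% | 1.3% |
| | 0.7 | 17.2% | 53.3% | 0.4% |
| One-way ANOVA, 6 × 3 | 0 | 23.3% | 21.5% | 5.0% |
| | 0.3 | 18.8% | 29.4% | 2.1% |
| | 0.5 | 16.1% | 39.7% | 0.9% |
| | 0.7 | 13.3% | 60.6% | 0.2% |

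The paired and repeated-measures versions keep type I error at 4.8–5.1%.

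At ρ = 0.5 with larger differences of 1.0 and 1.2 SD, ordinary against paired t-test power is 70% against 88% and 87% against 97% (n = 12), and 32% against 51% and 47% against 66% (n = 6).

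**Break-even.** For differences of 0.8–1.2 SD, the paired t-test overtakes the ordinary one at ρ of about 0.08–0.14 (n = 12) or 0.12–0.20 (n = 6). Repeated-measures ANOVA overtakes below 0.1.

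**Two-way ANOVA, direction only.** Let the variance shares be s (subject), c (subject-by-cycle) and e (residual), summing to 1, with T times. The true variance of a treatment difference is (2/n)(c + e/T). An ordinary analysis uses about (2/n)(s + c + e)/T. The test is therefore conservative when c < s/(T−1) and anti-conservative above that. With s assumed at 50%, the threshold is 50/2 = 25% for T = 3, 50/5 = 10% for T = 6 and 50/12 = about 4% for T = 13. No error rate is claimed, because variable selection comes before this test and the metabolite sampling times are not stated.

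**Whether other wording supplies pairing.** Pair-wise testing can mean two treatments at a time. Basal thiamine status adjusts for one measured characteristic and leaves other subject differences in the residual. Neither is a subject term.

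**Attribution.** This needs no arithmetic. Every sequence in 5.1 has thiamine in every cycle. After the baseline sample, the day advances and the fast lengthens to 4 h post-dose; then food is given (a meal in Part 1, a snack in Part 2). There is no thiamine-free cycle in which these changes occur without the vitamin.

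**The case against.** **The text never says unpaired.** A Student's t-test can be paired and an ANOVA can be repeated-measures. This is true, and one sentence could close the gap. But the plan names pairing elsewhere, including in the same section, and the tests taken at face value do not fit the design.

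**The loss depends on analysing levels.** If the treatment tests used change from each cycle's own baseline, a shared subject effect would cancel. At n = 12, δ = 0.8 and ρ = 0.3/0.5/0.7, unpaired power on change scores is 35.4/46.5/67.5% and paired power 32.7/43.1/63.4%, with type I error near 5% for both. That calculation is right, and on that reading pairing costs nothing to omit. However, the section speaks of comparing levels and does not specify change scores. This case corresponds to the near-zero correlation at which no loss is claimed, and paired tests on levels remain stronger at ρ = 0.5 and 0.7 (about 71% and 90% at n = 12).

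**The harm is bounded.** The t-test and one-way ANOVA err on the conservative side, the objective is secondary and exploratory in character, and the figures are per test before correction. All of this stands. It does not cover the two-way ANOVA, which can be anti-conservative.

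**Attribution is narrow.** Samples before 4 h are not affected by meals, and thiamine against thiamine plus inhibitor has a same-time control. Both points stand. Time of day and length of fast still change before 4 h, and the limitation concerns statements about thiamine itself.

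**The ranking point is editorial.** Agreed; it adds little weight.

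**Conclusion.** The concern holds and should be corrected. The size of the pairing loss rests on assumed correlations and effect sizes and applies only if ordinary tests are run on levels. At an assumed 0.8 SD and ρ = 0.5, power falls from 71% to 46% in Part 2, from 36% to 19% for the Part 1 t-test and from 40% to 16% for the Part 1 three-treatment ANOVA. True type I error is then about 1% instead of 5%. The loss is nil at ρ = 0 and grows with ρ. The direction of error for an ordinary two-way ANOVA is not fixed.

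The attribution point does not depend on any assumption about correlation: without a thiamine-free cycle, before-after change cannot be assigned to the vitamin. Neither issue touches the paired primary AUC analysis, and the attribution issue does not affect the inhibitor contrast.

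**What to change.** In Section 8.2, Analysis of Secondary Endpoint:

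- Name thiamine alone versus thiamine plus inhibitor, compared within subject at matched times, as the main metabolite contrast, and make the three ranking sentences agree with that.
- Replace the treatment tests with paired t-tests and repeated-measures ANOVA, treating both time and treatment as within-subject factors. Alternatively, use a mixed model with random subject and subject-by-cycle terms and fixed treatment, time, period and sequence.
- State whether the analysed variable is the level or the change from the cycle's baseline.
- Keep the multiplicity corrections already planned.
- Report post-dose change from baseline as descriptive change after dosing, without attributing it to thiamine.

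The cost is SAP wording and routine analysis code, with no new data, visits or samples. Section 5.1 takes trimethoprim into Part 2 on the basis of Part 1 results, so any change to the Part 1 tests should be labelled as made after those results.
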